SPIDER Study Protocol

Study Title

SPIDER – *Spinal Dural Arteriovenous Fistula International Data and Outcomes Registry*

Principal Investigator

[name], FAANS, FACS, FAHA

The [name] Distinguished Professor of Neurological Surgery and Radiology

Division Chief of Neurovascular Surgery & Endovascular Neurosurgery

Thomas Jefferson University Hospital

Study Coordinator / Contact

[name] [name]

Research Fellow, Department of Neurosurgery

Thomas Jefferson University Hospital

Study Version and Date

Version 1.0 – 20 December 2025

Background and Rationale

Spinal dural arteriovenous fistulas (SDAVFs, type I spinal vascular malformations) are the most common spinal vascular malformation but remain frequently underdiagnosed due to their insidious onset and nonspecific clinical presentation. Delayed diagnosis is common and often results in progressive, and sometimes irreversible, myelopathy. Despite advances in imaging and treatment, there remains significant variability in diagnostic timelines, treatment strategies (endovascular, surgical, or combined), and reported outcomes across institutions.

Existing literature is largely limited to single-center retrospective series or small cohorts, often underpowered to evaluate predictors of outcome, recurrence, and the impact of diagnostic delay. Furthermore, direct comparisons between treatment modalities and long-term functional outcomes using standardized clinical scales are limited.

The SPIDER registry is designed to address these gaps by creating the largest international, multicenter dataset of patients with spinal dural AVFs. By pooling de-identified data from high-volume centers worldwide, this study aims to provide robust, generalizable evidence to inform clinical decision-making and optimize patient outcomes.

Study Objectives

Primary Objectives

1. To characterize the clinical, radiological, and angiographic presentation of spinal dural AVFs.
2. To compare treatment strategies (endovascular, surgical, combined, or conservative management) and their angiographic and clinical outcomes.
3. To evaluate long-term neurological and functional outcomes following treatment.
4. To assess the impact of diagnostic delay on neurological status and long-term outcomes.

Secondary Objectives

- To identify factors associated with treatment failure or recurrence.
- To evaluate complication rates associated with different treatment modalities.

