 - Endovascular embolization alone
 - Open surgery alone
 - Combined approaches
 - Conservative management
- Endovascular details:

- Number of embolization attempts
- Embolic agent used
- Angiographic outcome
- Intra- or postprocedural complications
- Surgical details:
 - Intraoperative visualization modality
 - Indication for visualization
 - Surgical outcome (successful or unsuccessful disconnection)
 - Intra- or postoperative complications

Recurrence and Re-treatment

- Occurrence of recurrence
- Time to recurrence
- Treatment modality for recurrence
- Angiographic outcome after re-treatment

Follow-Up and Outcomes

- Duration of follow-up
- Symptom evolution at last follow-up (pain, sensory, motor)
- Modified Aminoff–Logue Scale (Gait and Bladder) at last follow-up
- Modified Rankin Scale at last follow-up
- Overall clinical status at last follow-up (improved, unchanged, worsened)
- Death, if applicable

Notes

- Additional relevant clinical or radiological comments

Outcomes

Primary Outcomes

- Functional outcome at last follow-up as measured by mRS and Modified Aminoff–Logue scales.
- Angiographic success (complete vs partial vs unsuccessful occlusion).

Secondary Outcomes

- Rate and predictors of recurrence.
- Complication rates by treatment modality.
- Association between diagnostic delay and neurological outcome.

Statistical Analysis Plan

Descriptive statistics will be used to summarize demographic, clinical, radiological, and treatment characteristics. Continuous variables will be reported as means with standard deviations or medians with interquartile ranges, as appropriate. Categorical variables will be reported as frequencies and percentages.

Comparative analyses will be performed to evaluate outcomes across treatment modalities using appropriate statistical tests (e.g., chi-square, t-test, ANOVA, or non-parametric equivalents). Multivariable regression models may be used to identify independent predictors of outcomes and recurrence.

Missing data will be handled using appropriate statistical methods depending on the extent and pattern of missingness.

Ethical Considerations

This study involves retrospective collection of **fully de-identified data** and poses minimal risk to participants. No direct patient contact will occur, and no protected health information will be shared.

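### The variable list does not record whether, when or why vascular imaging was done after treatment, so patients imaged and clear cannot be told from patients never imaged, and recurrence figures may partly reflect imaging practice

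*Protocol*

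**What the plan says.** The protocol's Secondary Outcomes include "Rate and predictors of recurrence", and a secondary objective is "To identify factors associated with treatment failure or recurrence". The protocol's statistical section adds: "Comparative analyses will be performed to evaluate outcomes across treatment modalities using appropriate statistical tests". Regression for predictors of recurrence is optional.

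The data come from the Recurrence and Re-treatment block of Data Collection and Variables. It has four items: "Occurrence of recurrence", "Time to recurrence", the modality used to treat the recurrence, and "Angiographic outcome after re-treatment". The Follow-Up and Outcomes block gives "Duration of follow-up", then symptoms, functional scales, overall status and death.

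Under Study Design, everything is taken from records that already exist. No follow-up imaging schedule is set.

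**The concern.** Some recurrences can be silent and visible only on imaging. For such an event, absence of a recorded recurrence means something only if someone looked. Two patients with five years of clinic follow-up, one with a clear late angiogram and one never re-imaged, can have identical entries in the listed fields.

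Two things are at stake. The overall recurrence rate may be too low. Any comparison by modality, centre or other factor linked to imaging habits may also mix recurrence with the chance of finding it. In a multi-country retrospective registry, imaging follows local practice, and the protocol's own rationale stresses variation between institutions.

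This is not detail that can wait for a statistical analysis plan, since no analysis can use a variable that was not collected.

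**Working it through.** **Step 1: does any listed field supply the information?**

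| Nearest field | Why it does not fill the gap |
|---|---|
| MRI findings | Listed with the radiological characteristics of the fistula, not with follow-up |
| Endovascular angiographic outcome | Listed under treatment details; no later imaging or date |
| "Surgical outcome (successful or unsuccessful disconnection") | Success of disconnection; the surgical block has no angiographic field |
| "Angiographic outcome after re-treatment" | Exists only once a recurrence is known and re-treated |
| "Duration of follow-up" | Overall length of follow-up, not time to last imaging |
| Notes | Free text, not systematic |

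None does. The protocol states no recurrence rate, imaging rate or sample size, so there is no figure to reproduce. Every rate and group size below is an assumption.

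**Step 2: how large could the distortion be?** Let r be true recurrence, i the share imaged, and d the share of unimaged recurrences that surface through symptoms. If patients with no recurrence found are analysed as recurrence-free:

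observed = r × [i + (1 − i) × d]

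Take r = 15% in both modalities, i = 80% in A and 40% in B.

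- d = 0: A = 15 × 0.8 = 12.0%; B = 15 × 0.4 = 6.0%. Ratio 2.0.
- d = 0.5: A = 15 × (0.8 + 0.2 × 0.5) = 13.5%; B = 15 × (0.4 + 0.6 × 0.5) = 10.5%. Ratio 1.29.

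**Step 3: other assumed values, with d = 0.**

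- r = 10%, imaging 90% vs 50%: 9.0% vs 5.0%, ratio 1.80. The chance of a falsely significant difference (two-sided 5% level) is about 35%, 48% and 70% with 200, 300 and 500 patients per group.
- r = 10%, imaging 90% vs 70%: 9.0% vs 7.0%, ratio 1.29. The corresponding chances are about 11%, 15% and 21%.
- r = 10%, imaging 80% in both: 8.0% vs 8.0%. There is no false difference, but both rates are understated.
- True rates 20% vs 10%, imaging 45% vs 90%: 20 × 0.45 = 9% and 10 × 0.90 = 9%. A real two-fold difference disappears.

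Missing imaging information can therefore create a difference or hide one.

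**Step 4: would the rate among all imaged patients solve it?** Use the d = 0.5 case per 100 patients, and assume symptomatic recurrences are confirmed by imaging.

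- A: symptom-detected 15 × 0.2 × 0.5 = 1.5; imaged 80 + 1.5 = 81.5; rate 13.5 / 81.5 = 16.6%.
- B: symptom-detected 15 × 0.6 × 0.5 = 4.5; imaged 40 + 4.5 = 44.5; rate 10.5 / 44.5 = 23.6%.

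The false gap grows from 3.0 to 7.0 percentage points and changes direction. Restricting to routinely imaged patients gives 12 / 80 = 15% and 6 / 40 = 15%, provided routine imaging is unrelated to recurrence within each modality. The reason for imaging therefore has to be recorded as well as its occurrence.

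**The case against.** The strongest objection concerns what may be inferred. A reader might conclude that never-imaged patients are counted as recurrence-free. The protocol does not say so. It refers to a common spreadsheet with preset categories that are not shown; the recurrence item might offer an unknown option, and the protocol provides for missing data in general terms. This stands. But an unknown option alone would not give the time of last imaging or how a recurrence was found.

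A reader might also infer that the more heavily imaged modality will appear to recur more. That follows when true recurrence is equal; the 9% vs 9% example shows it need not otherwise. The documents do not say that imaging differs by modality. The two-fold ratio further needs 80% vs 40% imaging and no detection through symptoms.

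Nor is the gap beyond later repair. Centre, country and year of treatment are collected, centres keep their own data, and cleaning is planned for 2026, so sites could be queried. Later correction would be costly, not impossible.

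Finally, recurrence is a secondary outcome, the functional primary outcomes do not depend on these fields, and no survival analysis or censoring rule is stated. The remark that overall follow-up is a poor censoring time matters only if the collected time to recurrence is analysed that way.

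These objections limit the claim. They do not supply the missing fields.

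**Conclusion.** The point holds as a gap in the protocol's variable list: the listed fields cannot separate imaged and clear from never imaged, and do not show how recurrences came to light. The recurrence rate may be understated, and associations with modality or other predictors may partly reflect imaging practice.

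The size and direction in this registry are unknown. The illustrations range from no false difference (equal imaging) to a false two-fold ratio. They rest on assumed true recurrence and imaging shares, and on patients with no recurrence found being analysed as recurrence-free. The documents do not support a claim that a bias of given size or direction will occur. The change should be made because a stated secondary outcome depends on it and it is cheapest before collection closes.

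**What to change.** Before the end-February 2026 collection deadline, add four columns to the spreadsheet:

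1. Follow-up vascular imaging after treatment: none / MRI or MRA / catheter angiography / unknown.
2. Time from treatment to the last such imaging.
3. Reason for that imaging: routine surveillance or symptoms.
4. How any recurrence was detected: surveillance imaging, or new or worse symptoms.

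State in Outcomes that:

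- the proportion imaged will be tabulated by modality and centre;
- symptomatic recurrence will be reported in all treated patients;
- recurrence in patients with routine surveillance imaging will be reported separately, with patients counted as recurrence-free only up to their last imaging;
- the rate in all imaged patients will not be the single main figure.

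The two recurrence figures should be read together. Routine imaging may find a recurrence before symptoms appear, and in the d = 0.5 case the symptom-detected counts alone are 1.5 vs 4.5 per 100 despite equal true recurrence.

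The cost is some extra abstraction from existing reports, possible re-extraction at centres that have already entered data (the protocol does not say how many) in an unfunded study with a short window, and a smaller denominator for imaging-based recurrence. The change records what was done and asks for no additional imaging.

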- To explore predictors of functional recovery using standardized outcome measures.

Study Design

This is an **international, multicenter, retrospective observational cohort study**.

Participating centers will contribute de-identified data on patients diagnosed with spinal dural arteriovenous fistulas who were evaluated and/or treated at their institution.

No interventions will be performed as part of this study. All data are derived from existing medical records, imaging, and procedural reports.

Study Population

Inclusion Criteria

- Patients of any age diagnosed with **spinal dural arteriovenous fistula (Type I)**.
- Diagnosis confirmed by spinal angiography, MRI findings consistent with SDAVF, and/or operative findings.
- Patients managed with endovascular treatment, open surgery, combined approaches, or conservative management.
- Both symptomatic and incidental/asymptomatic cases.

Exclusion Criteria

- Intramedullary spinal vascular malformations (e.g., glomus AVMs, juvenile AVMs).
- Perimedullary AVFs or other non-dural spinal vascular lesions.
- Cases lacking sufficient data to confirm diagnosis or treatment details.

Data Collection and Variables

Each participating center will extract data using a standardized spreadsheet with predefined categorical options to ensure consistency across sites. All data will be fully de-identified prior to submission.

Demographics and Center Information

- Country

- Study center (institution name)
- Patient study number
- Age at diagnosis
- Sex

Clinical History and Presentation

- Months from symptom onset to diagnosis
- Misdiagnoses prior to SDAVF diagnosis
- History of spinal trauma
- Incidental/asymptomatic presentation
- Presentation with rupture (spinal, intracranial, both, or none)
- Presence of myelopathy at diagnosis
- Presenting symptoms: back pain, radicular pain, sensory symptoms, motor weakness, spasticity

Functional Status at Diagnosis

- Modified Aminoff–Logue Scale (Gait)
- Modified Aminoff–Logue Scale (Bladder)
- Modified Rankin Scale (mRS)

Radiological and Angiographic Characteristics

- Laterality of fistula
- Spinal level of fistula (highest level if multilevel)
- Number of arterial feeders
- Highest and lowest arterial feeder levels (if multiple)
- Involvement of the artery of Adamkiewicz
- MRI findings (myelomalacia, cord edema, or T2 hyperintensity)

Treatment Details

- Year of treatment
- Time from diagnosis to first treatment
- Initial treatment modality:

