Each participating institution is responsible for obtaining local Institutional Review Board (IRB) or Ethics Committee approval or exemption, as required by local regulations.

Data will be securely stored and accessed only by authorized study investigators.

Data Sharing and Publication Policy

Contributing centers will retain ownership of their local data. Aggregated data will be used for pooled analyses, conducted at the main study center. All participating centers will have

the opportunity to submit project proposals to conduct analyses using the study database, subject to review and approval at the discretion of the main study center.

Authorship on resulting manuscripts will follow ICMJE guidelines and will include contributors from participating centers based on data contribution and intellectual involvement.

If enrollment targets are met, the SPIDER registry is expected to support multiple high-impact publications addressing clinical presentation, treatment strategies, radiological predictors, and outcomes.

Timeline

- Center enrollment and IRB approvals: Ongoing
- Data collection deadline: **End of February 2026**
- Data cleaning and analysis: 2026
- Manuscripts preparation and submission: 2026

Funding and Conflicts of Interest

This study is investigator-initiated and currently unfunded. Any potential conflicts of interest will be disclosed in resulting publications.

Conclusion

The SPIDER registry aims to establish the most comprehensive international dataset on spinal dural AVFs to date. By leveraging multicenter collaboration, this study seeks to generate high-quality evidence to improve diagnosis, treatment selection, and long-term outcomes for patients with this rare but debilitating condition.

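### The primary functional outcome is read at last follow-up with no minimum, common time point or definition of long-term, so unequal follow-up can pass for a treatment difference

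*Protocol*

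**What the plan says.** Under Outcomes, Primary Outcomes, the protocol lists "Functional outcome at last follow-up as measured by mRS" and the Modified Aminoff–Logue scales. This outcome has to serve three primary objectives (Study Objectives, Primary Objectives):

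- Objective 2: "To compare treatment strategies (endovascular, surgical, combined, or conservative management) and their angiographic and clinical outcomes".
- Objective 3: "To evaluate long-term neurological and functional outcomes following treatment".
- Objective 4: "To assess the impact of diagnostic delay on neurological status and long-term outcomes".

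Under Study Population, the only exclusion for insufficient data is "Cases lacking sufficient data to confirm diagnosis or treatment details"; it says nothing about length of follow-up. Data Collection and Variables asks for the mRS and the two Aminoff–Logue scores (gait and bladder) at two moments only: at diagnosis and at last follow-up. It also asks for "Duration of follow-up", the year of treatment, the time from diagnosis to first treatment, and death as a separate item. The Timeline gives "Data collection deadline: End of February 2026".

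The protocol's statistical section offers chi-square, t-test, ANOVA or non-parametric equivalents as examples for comparing modalities. Multivariable regression is optional, and no covariate is named.

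**The concern.** Last follow-up is not a point in time. Each patient supplies a reading at whatever interval the records happen to hold, and nothing prevents that interval from being a few weeks. Two things are at stake.

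First, the outcome does not ensure a long-term reading, although Objectives 3 and 4 ask for one. A pooled result would average over an unknown mix of early and late readings.

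Second, Objective 2 compares management groups. If functional status changes with time since treatment, and if groups, centres or treatment eras have different lengths of follow-up, part of any observed difference reflects when patients were seen. A larger registry does not remove this. It makes a spurious difference more likely to reach significance.

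**Working it through.** **What is fixed and what is not.** The protocol states no sample size, power, rate or follow-up figure, so there is nothing to reproduce. The first check is a reading of each place where timing could be set:

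| Place in the protocol | What it settles about timing |
|---|---|
| Primary Objectives 3 and 4 | Ask for long-term outcomes; the term is not defined |
| Inclusion and exclusion criteria | No minimum follow-up |
| Treatment Details | Year of treatment recorded; no first or last year set |
| Follow-Up and Outcomes | Duration recorded, without saying whether it runs from diagnosis or from treatment |
| Primary Outcomes | Last follow-up; no month, window or minimum |
| Statistical section | Simple tests as examples; optional regression; duration not mentioned |
| Timeline | Close at end of February 2026; no minimum interval after treatment |

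A patient treated shortly before the close and a patient followed for years therefore enter the primary outcome on equal terms.

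**How large the effect could be (assumed values).** Suppose treatments are identical, and 40% of patients are improved if last seen early (by 3 months) against 60% if last seen late (12 months or more). With a share *e* of a group seen only early:

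improved = *e* × 40% + (1 − *e*) × 60%

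spurious difference = (*e*₁ − *e*₂) × (60 − 40) points

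| Share seen only early, group 1 v group 2 | Improved, group 1 | Improved, group 2 | Difference |
|---|---|---|---|
| 30% v 20% | 12 + 42 = 54% | 8 + 48 = 56% | 2 points |
| 40% v 15% | 16 + 36 = 52% | 6 + 51 = 57% | 5 points |
| 50% v 10% | 20 + 30 = 50% | 4 + 54 = 58% | 8 points |

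The result is proportional to the assumed gap between early and late readings: halve the gap from 20 to 10 points and the range becomes 1 to 4 points.

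**A second assumed model, as a cross-check.** Let both groups share the recovery curve 0.60 × (1 − exp(−*t*/τ)), and let last follow-up be exponential with mean *m* months. The expected proportion improved is 0.60 × *m*/(*m* + τ). For mean follow-up of 12 v 24 months:

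| τ (months) | Mean 12 | Mean 24 | Difference | Chance of p < 0.05, 100 per group | 200 per group |
|---|---|---|---|---|---|
| 3 | 0.60 × 12/15 = 48.0% | 0.60 × 24/27 = 53.3% | 5.3 points | 11% | 19% |
| 6 | 0.60 × 12/18 = 40.0% | 0.60 × 24/30 = 48.0% | 8.0 points | 21% | 36% |
| 12 | 0.60 × 12/24 = 30.0% | 0.60 × 24/36 = 40.0% | 10.0 points | 32% | 56% |

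The true treatment difference is zero in every row. With equal mean follow-up (24 v 24 months), the expected difference is 0 and the error rate is the nominal 5%.

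**The case against.** The strongest reply is that the data set already holds much of the remedy. The scales are recorded at diagnosis as well as at last follow-up, so change from baseline can be analysed. Follow-up duration and year of treatment are collected, so patients can be restricted or the comparison adjusted by duration. Choosing covariates is ordinary work for a statistical analysis plan, which may exist but is not shown. In an unfunded chart review that closes about two months after its version date (20 December 2025), last follow-up is also a practical choice.

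Most of this stands, and it sets the limits of the point. The absence of a covariate list is not itself the defect. But the outcome definition and the collected variables are fixed in this protocol. A later plan could restrict or adjust by duration, but only if centres had measured it from the same origin, and it could not recover a score at a common time that was never extracted.

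Four stronger readings are tempting and are not supported:

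- A reader might infer that follow-up does differ between modalities. The protocol gives no follow-up figures by group.
- A reader might infer that Objective 3 cannot be answered. With duration recorded, long-term status can be described in those followed long enough.
- A reader might infer that recovered patients stop attending, or that early readings understate benefit. Both are plausible, but the protocol says neither.
- A reader might infer that the two scales handle death differently. Death is listed as a separate item, with no scoring rule for either scale.

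It is also fair to object to making a 12-month reading primary. Having a visit in a window can itself depend on outcome, the protocol does not equate 12 months with long-term, and some records will hold no such visit. A fixed-time score is therefore better as support.

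**Conclusion.** The point holds as a weakness in how the primary functional outcome is fixed, and it should be corrected. The outcome carries no minimum, common time or definition of long-term, and the one variable that could repair this has no stated origin and no stated use. Follow-up length can therefore be mistaken for a treatment effect.

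The size is not known. The 2 to 8 points rest on assumed rates of 40% and 60% and on assumed shares of early readings. They also use proportion improved as a simple stand-in for the scale scores. The second model's 5.3 to 10.0 points rest on an assumed curve, follow-up distribution and group sizes. Both show direction and possible size only, and both vanish if status does not change with time or if follow-up is alike across groups. The registry remains usable; it is the claim to a long-term, between-group functional comparison that needs support.

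**What to change.** 1. State the time origin of follow-up duration: first treatment, or diagnosis for conservatively managed cases. Note as a limitation that these clocks differ. Because time from diagnosis to first treatment is already collected, a sensitivity analysis can put all patients on the diagnosis clock.
2. Define long-term, and restrict the long-term functional analysis to patients whose last reading is at or beyond a stated minimum (for example 6 or 12 months). Keep earlier deaths in that analysis, and state one rule for death that applies to both scales.
3. Report follow-up duration by treatment group. Compare groups with a model for the last score that includes follow-up duration and the score at diagnosis, in place of unadjusted tests alone.
4. Where records allow, add the scores and the month of the visit nearest 12 months, as a supportive fixed-time analysis.

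Items 1 to 3 use variables already on the collection list, although centres must confirm which origin they used. Item 4 needs a few more columns from existing notes and is easiest before the data close. The cost is fewer patients in the long-term analysis and a little more extraction. Patients below the minimum stay in the descriptive summaries and in an all-patient sensitivity analysis. Adjustment will not remove bias if the timing of the last visit depends on how the patient is doing, so that should be stated as a limitation.

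### For initial treatment, the three-level angiographic primary outcome is listed as a data item only for embolisation, so it cannot be compared across the four strategies as defined

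*Protocol*

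**What the plan says.** Primary Objective 2 (Study Objectives) is "To compare treatment strategies (endovascular, surgical, combined, or conservative management) and their angiographic and clinical outcomes".

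The Outcomes section lists two primary outcomes. One is "Functional outcome at last follow-up as measured by mRS and Modified Aminoff–Logue scales". The other is "Angiographic success (complete vs partial vs unsuccessful occlusion", with three levels and no restriction by modality.

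The Statistical Analysis Plan section adds: "Comparative analyses will be performed to evaluate outcomes across treatment modalities using appropriate statistical tests".

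Under Data Collection and Variables, Treatment Details, the item "Angiographic outcome" appears among the endovascular details, without its levels. The surgical details have instead "Surgical outcome (successful or unsuccessful disconnection". "Conservative management" is one of the four initial modalities but has no outcome item of this kind. Recurrence and Re-treatment lists "Angiographic outcome after re-treatment". Follow-Up and Outcomes lists symptoms, the functional scales, overall clinical status and death, and nothing angiographic.

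**The concern.** A primary outcome that is to be compared between groups has to be measured on the same scale, and in a comparable way, in each group. Here the listed items differ by treatment. Embolised patients have an angiographic result. Surgical patients have a yes/no statement about disconnection, and the protocol does not say whether it rests on intraoperative visualisation, the surgeon's judgement or a later angiogram. No listed item records whether vascular imaging was done after treatment.

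A comparison of embolisation with surgery on these items would mix the effect of treatment with the effect of how success was recorded, and the data could not separate the two. This concerns one of the two primary outcomes, in a registry that is meant to guide the choice between treatments.

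**Working it through.** The protocol states no sample size, rate or power for this outcome, so there is no figure to reproduce. The check sets the outcome definition against the listed items for each initial strategy.

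| Initial strategy | Listed item on success of initial treatment | Can the three levels be filled? |
|---|---|---|
| Embolisation alone | Angiographic outcome | Yes, assuming that its options are the three levels of the primary outcome |
| Open surgery alone | Disconnection, two levels | No: partial cannot be derived, and the item is not defined as angiographic |
| Combined | Both of the above | Not without a rule for merging them; none is given |
| Conservative | None | No: there is no treatment whose occlusion result could be graded |

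Direct support: 1 of 4 strategies.

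Three possible rescues were then considered.

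1. *The re-treatment item.* It is not tied to one modality, so some surgical patients would acquire an angiographic result. It applies only to recurrences that were treated again, and describes the result of the second treatment. It does not supply the initial result.

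2. *Collapsing to two levels.* Let the shares of complete, partial and unsuccessful results after embolisation be c, p and u, with c + p + u = 1. Success is c if partial counts as failure, and c + p if it counts as success. The two choices differ by (c + p) − c = p. The surgical success share does not move, because that item has no partial level, so the embolisation-minus-surgery difference also shifts by exactly p. The protocol gives no value for p, so the size of the shift is unknown. A rule would fix the choice, but the comparison would still set an angiographic result against a disconnection result.

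3. *Missing-data methods.* The Statistical Analysis Plan section promises suitable handling of missing data. If an item is not collected at all in the surgery-alone group, nothing within that group informs its distribution, and borrowing it from embolised patients would assume the answer to the comparison.

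None of the three restores the comparison as defined.

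**The case against.** The strongest reply has four parts.

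- *The list may not be the whole data set.* Centres work from a standardised spreadsheet that is not shown, and it may hold a post-surgical imaging field. This stands as a limit: the finding is that the item is not in the protocol's variable list, not that it is proven absent from the spreadsheet. If the spreadsheet has it, the protocol's list needs correcting.

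- *Mapping of levels belongs in a statistical analysis plan.* This is fair for the rule on partial results, whose absence here is not the defect. It does not answer the main point, because an analysis plan can recode what was collected but cannot create what was not.

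- *Conservative cases are not lost data.* Agreed. Occlusion is not a meaningful outcome for them, and one clarifying sentence is enough.

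- *Not everything in Objective 2 fails.* Agreed. A reader might infer that the primary comparison as a whole cannot be made. The document does not support that: the mRS and Aminoff–Logue items are listed for all patients whatever the modality, so the clinical half stands. A two-level comparison of embolisation with surgery is also arithmetically possible, though like is not shown to be compared with like. Nor does the protocol commit to a particular test for this outcome; its tests are given only as examples.

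**Conclusion.** The point holds for initial treatment. One of the two primary outcomes can be filled directly, from the listed items, for one of the four strategies that Objective 2 compares. The angiographic half of that objective cannot be delivered as defined, while the functional primary outcome is untouched.

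The conclusion rests on two assumptions: that the variable list reflects what centres extract, and that the endovascular item uses the three levels of the primary outcome. It depends on no assumed rate. A reader might want a figure for the bias, but the document gives nothing from which to calculate one.

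It should be settled before data collection closes, because the gap lies in what is extracted and not in how it is analysed.

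**What to change.** Before the end-February 2026 deadline (Timeline), add one common item for every treated patient, whether endovascular alone, surgery alone or combined. It is filled from existing records after completion of the initial treatment and asks for no new imaging:

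- post-treatment vascular imaging done: yes or no;
- modality;
- time from treatment;
- result: complete, partial, unsuccessful or not imaged.

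Then state in Outcomes that the three-level result is compared among the treated groups, that the not-imaged share is reported by group, that surgical disconnection is a separate descriptive item, and that conservative cases are outside this outcome. Reword Objective 2 to match.

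If re-extraction is not feasible, restrict the three-level outcome to the groups where it is recorded, report surgical disconnection separately, and make no claim of a cross-modality angiographic comparison.

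*Cost.* The first option means a few spreadsheet columns and a return to some charts, in an unfunded study with little time: from the protocol date of 20 December 2025 to 28 February 2026 is 11 + 31 + 28 = 70 days. The comparable denominator will shrink where surgical patients were not imaged. If imaging after surgery was selective, for instance prompted by poor recovery, the imaged patients will not represent the group; the not-imaged shares reveal this risk but do not remove it. The second option costs almost no work but gives up the angiographic half of Objective 2.
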